5.3 Secondary Efficacy Endpoints

5.3.1 Mild to Severe CIPN

Proportion of patients (with mild, moderate or severe chronic CIPN) scoring 2, 3, or 4, in at least 1 of the first 4 items of the FACT/GOG-NTX-13 (i.e. FACT/GOG-NTX-4), targeting numbness, tingling or discomfort in hands and/or feet, 9 months after the first dose of IMP.

Baseline is defined as the time of administration of the first dose of IMP (Day 1, Cycle 1).

Mild to Severe CIPN will derived (SAS) as follows:

```
cipn2=0;  
IF ntx1_std=. AND ntx2_std=. AND ntx3_std=. AND ntx4_std=. THEN cipn2=.;  
ELSE IF ntx1_std IN('2','3','4') OR ntx2_std IN('2','3','4') OR  
      ntx3_std IN('2','3','4') OR ntx4_std IN('2','3','4') THEN cipn2=1;
```

Mild to Severe CIPN will be analysed using the method of Cochran-Mantel-Haenszel as described in detail in Section 5.1.1.

Data Presentations

- Table: the analysis of Mild to Severe CIPN based on the negative binomial regression model will be presented by number of patients (N), treatment estimates and its 95% CIs. The rate ratio between PledOx 5 $\mu\text{mol/kg}$ and Placebo will be presented by the estimate, 95% CI and p-value.
- Table: the number and percentage of patients with Mild to Severe CIPN along with its 95% CI presented by treatment group and total for each treatment visit/assessment visit. The confidence intervals will be based on the method of Clopper-Pearson (exact).
- Figure: the proportion (including 95% CIs) of patients with Mild to Severe CIPN will be graphically depicted (lineplot) vs treatment cycle/assessment visit by treatment group.
- All observed values of Mild to Severe CIPN will be listed by patient.

All the analyses of Mild to Severe CIPN will be based on the observed cases. Hence, no imputation of missing values will be done.

5.3.2 Cold Sensitivity

Mean change from baseline in sensitivity to touching cold items on day 2, Cycle 4 of mFOLFOX6 chemotherapy, as assessed by the Cold Sensitivity questionnaire (ordinal scale 0-10).

Baseline is defined as the Screening measurement.

Analysis of Covariance. Cold Sensitivity will be analysed by Analysis of Covariance (ANCOVA) using the cold sensitivity baseline value as a continuous covariate and study (POLAR-A / POLAR-M), region (Asia / non-Asia) and treatment as factors. Least square means and its corresponding 95% confidence intervals will be presented.

Data Presentations

- Table: the analysis cold sensitivity based on the ANCOVA model will be presented by number of patients (N), estimate (LSM) and 95% CI for each treatment group. The treatment contrast (PledOx 5 µmol/kg vs Placebo) will be presented by estimate (difference in LSM), 95% CI and p-value.
- Table: descriptive statistics of observed values of cold sensitivity by treatment and total for each visit (baseline (screening), cycle 2,4 and 8) and measurements within each treatment visit (pre-infusion day 1, post-infusion day 1, post-infusion day 2 and, post-infusion day 3).
- Figure: shift plot (with jitter) of cold sensitivity at baseline vs cycle 4, day 2

The same output (except for the ANCOVA analysis) will be produced also for the other 3 variables included in the Cold Sensitivity questionnaire:

- Swallowing cold liquids
- Throat discomfort
- Muscle cramps

5.3.3 Cumulative Dose of Oxaliplatin

Mean cumulative dose of oxaliplatin administered per patient during mFOLFOX6 chemotherapy, 9 months after the first dose of IMP. Summary statistics of oxaliplatin related variables are presented in Section 4.4.2.

In case the patient receives more than 12 cycles of oxaliplatin, that will also be accounted for when deriving the cumulative dose.

Analysis of Variance. Mean cumulative dose of oxaliplatin will be analysed by Analysis of Variance (ANOVA) using study (POLAR-A / POLAR-M), region (Asia / non-Asia) and treatment as factors. Least square means and its corresponding 95% confidence intervals will be presented.

Data presentation

- Table: ANCOVA analysis - Number of patients (N), Point Estimate (LSM), 95% CI and P-value by treatment group/treatment comparison (PledOx 5 µmol/kg vs Placebo).

All observed values of mean cumulative dose of oxaliplatin will also be listed by patient.

5.3.4 Vibration Sensitivity Test

Mean change from baseline in vibration sense (0-8 ordinal scale), on the lateral malleolus (left and right), using a graduated tuning fork, at 9 months after the first dose of IMP.

Baseline is defined as the time of administration of the first dose of IMP (Day 1, Cycle 1).

Analysis of Covariance. Vibration sense will be analysed by Analysis of Covariance (ANCOVA) using the vibration sense baseline value as a continuous covariate and study (POLAR-A / POLAR-M), region

(Asia / non-Asia) and treatment as factors. Least square means and its corresponding 95% confidence intervals will be presented.

Data presentations

- Table: ANCOVA analysis - Number of patients (N), Point Estimate (LSM), 95% CI and P-value by treatment group/treatment comparison (PledOx 5 µmol/kg vs Placebo)
- Table: descriptive statistics of observed values by treatment and total for each treatment cycle
- Table: descriptive statistics of change from baseline by treatment and total for each treatment cycle
- Figure: shift plot (using jitter) of baseline vs 9-month assessment visit

All observed values of Vibration Sensitivity Test will also be listed by patient.

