3.1 Analysis Sets

The analysis set “All randomised patients (ITT)” consists of all patients who were assigned a randomisation number, irrespective of the treatment they received, if any.

The modified ITT (mITT) analysis set includes patients that fulfil at least one of the following criteria:

1. the patient was randomised prior to December 1, 2019 (ie the patient was eligible for at least 3 months of IMP) and had at least one post-baseline assessment for efficacy, or
2. the 3 month Assessment Visit occurred prior to 1 March, 2020, or
3. the patient received the 6th cycle of IMP after 1 March, 2020.

Patients will be analysed according to the treatment they are assigned to at randomisation, irrespective of what treatment they actually received.

The safety analysis set (SAF) consists of all randomised patients who receive at least one dose of IMP. Patients will be analysed according to the randomised study treatment actually received.

The list of patients to be included in each of the analysis sets is to be agreed between the project statistician and the Sponsor prior to unblinding, once all study data is available.

All enrolled patients will be listed indicating their membership to each analysis set along with the reason for exclusion.

The PK population (POLAR-M only) includes a subset of patients at pre-selected sites in all participating regions, where blood samples will be collected for pharmacokinetics and ECG assessments.

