5.3.5 Pain (NRS)

Mean change from baseline in worst pain in hands or feet in the past week, using a numerical rating scale (NRS), at 9 months after the first dose of IMP. NRS is measured on an ordinal scale 0-10.

Baseline is defined as the time of administration of the first dose of IMP (Day 1, Cycle 1).

Analysis of Covariance. Pain will be analysed by Analysis of Covariance (ANCOVA) using the pain baseline value as a continuous covariate and study (POLAR-A / POLAR-M), region (Asia / non-Asia) and treatment as factors. Least square means and its corresponding 95% confidence intervals will be presented.

Data presentations

- Table: ANCOVA analysis - Number of patients (N), Point Estimate (LSM), 95% CI and P-value by treatment group/treatment comparison (PledOx 5 µmol/kg vs Placebo).
- Table: descriptive statistics of observed values by treatment and total for each treatment cycle.
- Table: descriptive statistics of change from baseline by treatment and total for each treatment cycle.
- Figure: shift plot (using jitter) of baseline vs 9-month assessment visit.

All observed values of worst pain in hands or feet will also be listed by patient.

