5.3.6 Grooved Pegboard

Mean change from baseline in the time (seconds) to complete the Grooved Pegboard with the non-dominant hand, at 9 months after the first dose of IMP.

Baseline is defined as the time of administration of the first dose of IMP (Day 1, Cycle 1).

Analysis of Covariance. Grooved pegboard will be analysed by Analysis of Covariance (ANCOVA) using the grooved pegboard baseline value as a continuous covariate and study (POLAR-A / POLAR-M), region (Asia / non-Asia) and treatment as factors. Least square means and its corresponding 95% confidence intervals will be presented.

Data presentations

- Table: ANCOVA analysis - Number of patients (N), Point Estimate (LSM), 95% CI and P-value by treatment group/treatment comparison (PledOx 5 µmol/kg vs Placebo).
- Table: descriptive statistics of observed values by treatment and total for each treatment cycle.
- Table: descriptive statistics of change from baseline by treatment and total for each treatment cycle.
- Figure: shift plot (using jitter) of baseline vs 9-month assessment visit.

- Figure: scatter plot (using jitter) by treatment group for each treatment cycle.

All observed values of grooved pegboard will also be listed by patient.

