5.4.2 Mean Score of FACT/GOG NTX1-4

Mean score of the first 4 items of the FACT/GOG-NTX-13 (i.e. FACT/GOG-NTX-4), at 9 months after the first dose of IMP.

Baseline is defined as the time of administration of the first dose of IMP (Day 1, Cycle 1).

Analysis of Covariance. Mean score of FACT/GOG NTX1-4 will be analysed by Analysis of Covariance (ANCOVA) using the baseline value as a continuous covariate and study (POLAR-A / POLAR-M), region (Asia / non-Asia) and treatment as factors. Least square means and its corresponding 95% confidence intervals will be presented.

Data presentations

- Table: ANCOVA analysis - Number of patients (N), Point Estimate (LSM), 95% CI and P-value by treatment group/treatment comparison (PledOx 5 µmol/kg vs Placebo).
- Table: descriptive statistics of observed values by treatment and total for each treatment cycle.
- Table: descriptive statistics of change from baseline by treatment and total for each treatment cycle.
- Figure: shift plot of baseline vs 9-month assessment visit.

All observed values of the Mean Score of FACT/GOG NTX1-4 will also be listed by patient.

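### Five month-9 continuous endpoints rest on a single-visit ANCOVA with no missing-data method; a repeated-measures model would use the earlier values, for a modest gain in precision and, in some settings, less bias

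*SAP*

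**What the plan says.** Section 5.3.4 sets the vibration endpoint as change from baseline, "using a graduated tuning fork, at 9 months after the first dose of IMP", and fixes the model: "Vibration sense will be analysed by Analysis of Covariance (ANCOVA) using the vibration sense baseline value as a continuous covariate", with study, region and treatment as factors. There is no visit term and no within-patient correlation.

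The same model, at the same single time point, is set for:
- pain (5.3.5): "Pain will be analysed by Analysis of Covariance (ANCOVA) using the pain baseline value as a continuous covariate"
- pegboard (5.3.6): "Grooved pegboard will be analysed by Analysis of Covariance (ANCOVA) using the grooved pegboard baseline value as a continuous covariate"
- the four-item neurotoxicity mean (5.4.2): "Mean score of FACT/GOG NTX1-4 will be analysed by Analysis of Covariance (ANCOVA) using the baseline value as a continuous covariate"
- the 13-item mean (5.4.3), in matching terms.

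Each of these five sections also plans summaries at earlier occasions, for example "descriptive statistics of change from baseline by treatment and total for each treatment cycle". Those values are used only descriptively.

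Efficacy is analysed in the modified ITT set (Section 5). Its first route in Section 3.1 asks that the patient "had at least one post-baseline assessment for efficacy". The other two routes are a 3-month visit before 1 March 2020 and a sixth cycle of study drug after that date. None requires a month-9 value.

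On missing data, Section 5.2 covers the primary endpoint only. Section 3.3 expects missing observations but gives rules only for baseline values and incomplete dates. Section 3.4 moves unscheduled measurements to the nearest Assessment Visit and places in-window discontinuation visits at a scheduled visit.

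**The concern.** A single-visit ANCOVA without imputation uses only patients with a value at that visit. The SAP does not say this for the five endpoints, but it follows from the model. The analysis set is therefore defined more widely than the model can use, and post-baseline scores already collected do not inform the month-9 comparison.

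Two things are at stake. The first is precision, because an earlier score partly predicts the missing month-9 score. The second is validity. A completers-only ANCOVA needs missingness at month 9 to be unrelated to the outcome once baseline, arm, study and region are accounted for. A repeated-measures model also allows missingness to depend on recorded post-baseline scores.

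**Working it through.** **The plan's own figures.** The only design figures concern the binary primary endpoint: 112 per group for 40% versus 20%, two-sided 0.05. They reproduce: power is 0.9096 against the stated 91%, and 112 / (1 - 0.20) = 140 per arm. No SD, between-visit correlation or month-9 missing rate is given for any continuous endpoint, so the rest is a calculation under stated assumptions.

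**How many patients.** At the planning dropout of 20%, 0.20 × 140 = 28 per arm would be absent at month 9. For the combined 5 µmol/kg versus placebo comparison, randomised numbers give about 301/2 + 290/3 = 247 per arm, and 0.20 × 247 ≈ 49. This approximates from all randomised patients, because the modified ITT size is not stated.

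**Precision.** Let m be the fraction missing at month 9. Let r be the correlation between the earlier and the month-9 value after adjustment for baseline, since both models adjust for it. With values missing at random positions and one earlier visit always seen, the variance ratio of repeated measures to completers-only ANCOVA is

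[1 + (m/(1 - m))(1 - r²)] × (1 - m) = 1 - m·r².

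If the plain correlation is ρ and both visits correlate 0.4 with baseline, r = (ρ - 0.16)/(1 - 0.16).

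| ρ | r | r² | reduction, m = 0.2 | reduction, m = 0.3 |
|---|---|---|---|---|
| 0.5 | 0.34/0.84 = 0.405 | 0.164 | 3.3% | 4.9% |
| 0.7 | 0.54/0.84 = 0.643 | 0.413 | 8.3% | 12.4% |

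At 20% missing the standard error falls by 1 - √0.967 = 1.7% to 1 - √0.917 = 4.2%.

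**Bias.** Simulation, 600 replicates per scenario:
- SD 1, true effect -0.20 SD, lower scores better
- baseline correlation 0.4; earlier visit always observed and correlated 0.4, 0.6 or 0.8 with month 9
- where dropout depends on the earlier score, its log-odds rise by 1 per SD of that score.

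With 140 per arm, the ANCOVA bias in SD units was:

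| Missingness at month 9 | ρ = 0.4 | 0.6 | 0.8 |
|---|---|---|---|
| 20% in each arm, unrelated to scores | 0.004 | 0.000 | 0.007 |
| 20% in each arm, same dependence on earlier score | -0.009 | 0.003 | 0.004 |
| 20% in each arm, dependence in active arm only | -0.040 | -0.077 | -0.119 |
| 10% vs 30%, unrelated to scores | -0.002 | 0.005 | 0.010 |
| 10% vs 30%, same dependence | -0.041 | -0.079 | -0.103 |

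The repeated-measures estimate stayed within 0.01 SD of the truth in every row. Bias therefore needs both conditions: missingness must depend on earlier scores, and the rate or the mechanism must differ by arm. In these examples the negative sign flatters the active arm.

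**The case against.** The other side has a good deal to say.

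- **Why values are missing.** A reader might infer that patients leave because of progression, allergic reactions or neuropathy already visible in earlier scores. The SAP does not document that. Section 4.1 only lists possible withdrawal reasons, without frequencies, and separates stopping study drug from leaving the study. Section 1 also points to calendar effects: dosing held on 1 March 2020 and a data cut-off targeted for the third quarter of 2020. Nine months after 1 December 2019 is about 1 September 2020, so some values may be missing for administrative reasons. Such loss would probably be similar in both arms, and then neither method is biased. This stands.
- **Size of the gain.** A reader might put the plain correlations of 0.5 and 0.7 into 1 - m·r² and get 5-10% at 20% missing. That overstates the gain, because ANCOVA already takes the part that baseline explains. The 20% is also a planning figure for randomised patients, not a rate for the modified ITT set. This stands.
- **Earlier values for everyone lost.** The first modified ITT route asks for any efficacy assessment, not for one of these tests, and the visit schedule is in the protocol. How many of the excluded patients have usable earlier scores cannot be counted from the SAP. This stands, but all five sections plan per-cycle tables, so earlier values are expected.
- **Section 3.4.** Reallocation returns a month-9 value to some patients. It does so only for unscheduled or in-window discontinuation measurements.
- **Legitimacy.** A baseline-adjusted ANCOVA at the defined visit is an accepted analysis, and these endpoints are secondary or exploratory. That limits the weight of the point but does not remove it.

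**Conclusion.** The point holds in a limited form. Five endpoints are analysed from month-9 completers with no missing-data method, while earlier recorded values are left unused. Under the assumptions above, a repeated-measures model would cut variance by about 3-8% at 20% missing and 5-12% at 30%. It would also remove bias of roughly 0.04 to 0.12 SD at 20% missing in the settings where dropout follows earlier scores in one arm only.

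It would be too strong to conclude that the planned ANCOVA is biased in this trial, or that the model would cure dropout. It does not cure informative missingness, where the unseen month-9 score itself drives the loss. If loss is mainly administrative, only precision is gained. All sizes rest on assumed missing rates and correlations.

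The point does not extend to cold sensitivity (measured at Cycle 4) or to the cumulative doses of oxaliplatin and 5-FU. The formal testing procedure in Section 3 covers the primary endpoint alone, so only the estimates and intervals of these five endpoints, and the related month-12 ones, are affected.

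**What to change.** For Sections 5.3.4, 5.3.5, 5.3.6, 5.4.2 and 5.4.3, make the main analysis a mixed model for repeated measures:
- **Visits:** a limited set at which the test is recorded, for example the Assessment Visits up to month 12 and at most one or two on-treatment visits. All 12 cycles plus four Assessment Visits would need 16 × 17/2 = 136 unstructured covariance parameters; six occasions need 6 × 7/2 = 21.
- **Terms:** treatment-by-visit, baseline-by-visit, study and region.
- **Covariance:** unstructured, with a named fallback if the model does not converge, for example heterogeneous Toeplitz, then compound symmetry with a robust variance estimator.
- **Contrast:** 5 µmol/kg versus placebo at month 9. For pain and pegboard, take the month-12 contrasts of Sections 5.4.8 and 5.4.9 from the same model.
- **Sensitivity:** keep the planned ANCOVA, and state that it uses observed month-9 values only, including those placed there by Section 3.4.

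The cost is SAP wording and modest programming, with no new data. The price in assumptions is reliance on missingness at random given the recorded scores. Section 1 has the SAP finalised before unblinding, so a change made by then is still pre-specified.

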5.3.5 Pain (NRS)

Mean change from baseline in worst pain in hands or feet in the past week, using a numerical rating scale (NRS), at 9 months after the first dose of IMP. NRS is measured on an ordinal scale 0-10.

Baseline is defined as the time of administration of the first dose of IMP (Day 1, Cycle 1).

Analysis of Covariance. Pain will be analysed by Analysis of Covariance (ANCOVA) using the pain baseline value as a continuous covariate and study (POLAR-A / POLAR-M), region (Asia / non-Asia) and treatment as factors. Least square means and its corresponding 95% confidence intervals will be presented.

Data presentations

- Table: ANCOVA analysis - Number of patients (N), Point Estimate (LSM), 95% CI and P-value by treatment group/treatment comparison (PledOx 5 µmol/kg vs Placebo).
- Table: descriptive statistics of observed values by treatment and total for each treatment cycle.
- Table: descriptive statistics of change from baseline by treatment and total for each treatment cycle.
- Figure: shift plot (using jitter) of baseline vs 9-month assessment visit.

All observed values of worst pain in hands or feet will also be listed by patient.

5.3.6 Grooved Pegboard

Mean change from baseline in the time (seconds) to complete the Grooved Pegboard with the non-dominant hand, at 9 months after the first dose of IMP.

Baseline is defined as the time of administration of the first dose of IMP (Day 1, Cycle 1).

Analysis of Covariance. Grooved pegboard will be analysed by Analysis of Covariance (ANCOVA) using the grooved pegboard baseline value as a continuous covariate and study (POLAR-A / POLAR-M), region (Asia / non-Asia) and treatment as factors. Least square means and its corresponding 95% confidence intervals will be presented.

Data presentations

- Table: ANCOVA analysis - Number of patients (N), Point Estimate (LSM), 95% CI and P-value by treatment group/treatment comparison (PledOx 5 µmol/kg vs Placebo).
- Table: descriptive statistics of observed values by treatment and total for each treatment cycle.
- Table: descriptive statistics of change from baseline by treatment and total for each treatment cycle.
- Figure: shift plot (using jitter) of baseline vs 9-month assessment visit.

- Figure: scatter plot (using jitter) by treatment group for each treatment cycle.

All observed values of grooved pegboard will also be listed by patient.

5.3.7 Long-term Moderate to Severe CIPN

Long-term Moderate to Severe CIPN is defined as the proportion of patients scoring 3 or 4 in at least 1 of the first 4 items of the FACT/GOG-NTX-13 (i.e. FACT/GOG-NTX-4), targeting numbness, tingling or discomfort in hands and/or feet 12 months after the first dose of IMP.

Baseline is defined as the time of administration of the first dose of IMP (Day 1, Cycle 1).

Moderate to Severe CIPN will derived (SAS) as follows (same as primary endpoint):

```
cipn=0;  
IF ntx1_std=. AND ntx2_std=. AND ntx3_std=. AND ntx4_std=. THEN cipn=.;  
ELSE IF ntx1_std IN('3','4') OR ntx2_std IN('3','4') OR  
      ntx3_std IN('3','4') OR ntx4_std IN('3','4') THEN cipn=1;
```

Long-term Moderate to Severe CIPN will be analysed using the method of Cochran-Mantel-Haenszel as described in detail in Section 5.1.1.

All the analyses of Long-term Moderate to Severe CIPN will be based on observed cases. Hence, no imputation of missing values will be done.

Data Presentations

- Table: the analysis of Long-term Moderate to Severe CIPN based on the negative binomial regression model will be presented by number of patients (N), treatment estimates and its 95% CIs. The rate ratio between PledOx 5 µmol/kg and Placebo will be presented by the estimate, 95% CI and p-value.

5.4 Exploratory Endpoints

5.4.1 Any CIPN

Any CIPN is defined as the proportion of patients with any CIPN scoring 1, 2, 3 or 4, in any of the first 4 items of the FACT/GOG-NTX-13 (i.e. FACT/GOG-NTX-4), targeting numbness, tingling or discomfort in hands and/or feet, at all other timepoints after the first dose of IMP.

Baseline is defined as the time of administration of the first dose of IMP (Day 1, Cycle 1).

Any CIPN will derived (SAS) as follows:

```
cipn3=0;  
IF ntx1_std=. AND ntx2_std=. AND ntx3_std=. AND ntx4_std=. THEN cipn3=.;  
ELSE IF ntx1_std IN('1','2','3','4') OR ntx2_std IN('1','2','3','4') OR  
      ntx3_std IN('1','2','3','4') OR ntx4_std IN('1','2','3','4') THEN  
cipn3=1;
```

Data Presentations

- Table: the number and percentage of patients with Any CIPN along with its 95% CI presented by treatment group and total for each treatment visit/assessment visit. The confidence intervals will be based on the method of Clopper-Pearson (exact)
- Figure: the proportion (including 95% CIs) of patients with Any CIPN will be graphically depicted (lineplot) vs treatment cycle/assessment visit by treatment group.
- All observed values of Any CIPN will be listed by patient

The analysis of Any CIPN will be based on observed cases. Hence, no imputation of missing values will be done.

